9.3.2.1.7. Placental Abruption

Placental abruption (ICD-10-CM O45.X) will be identified by searching the mother's claims from 20 weeks gestation through the date of delivery.

9.3.2.2. Pregnancy Complications and Outcomes (Secondary Objective 2)

The pregnancy outcomes to be evaluated include live birth, non-live birth (stillbirth, and spontaneous abortion). A stillbirth is defined as a spontaneous (non-deliberate) fetal death that occurs at or after 20 weeks' gestation but prior to delivery. A spontaneous abortion is defined as a spontaneous (non-deliberate) embryonic or fetal death that occurs prior to 20 weeks' gestation. Placental abruption (ICD-10-CM O45.X) will be identified by searching the mother's claims from 20 weeks gestation through the date of delivery. Preeclampsia and eclampsia (ICD-10-CM O11.X, O14.X, O15.X) will be identified by searching the mother's claims from 20 weeks gestation through the date of delivery. A prior study conducted at one U.S. hospital found that the sensitivity of preeclampsia and eclampsia inpatient codes are generally low, however the PPV and specificity were high [Labgold, 2021].

Pregnancy outcomes will be identified in claims data through diagnosis and procedure codes (Appendix E. Live Birth Diagnosis and Procedure Codes and Appendix H. Spontaneous Abortion and Stillbirth Codes). Pregnancy episodes resulting in a live birth will be identified using validated algorithms (see Section 9.2.1.1) that have been used in Sentinel and non-Sentinel projects [Andrade, 2012; Andrade, 2016; Johnson, 2013; Sentinel Initiative, 2018]. Pregnancy episodes ending in a non-live birth pregnancy outcome will be identified using algorithms developed through Sentinel and non-Sentinel (e.g., VSD) projects [Andrade, 2021; Naleway, 2021].

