Wherever appropriate, the Mantel-Haenszel Chi-square test or Fisher exact test (univariate analysis) will compare the prevalence of each infant/birth outcome (MCMs and secondary outcomes of interest) between eligible live birth pregnancies among women with IC conditions who were vaccinated or not vaccinated with HZ/su during pregnancy. Multivariable conditional logistic regression will be conducted to adjust for potential residual confounding after matching if there is statistical significance in univariate analysis. In addition, the prevalence of each outcome and their associated 95% confidence intervals (CIs) will be calculated among women with IC conditions who were exposed to HZ/su during pregnancy versus corresponding matched women who were not exposed to HZ/su during pregnancy. All analyses will be stratified by stage of pregnancy (pre-pregnancy, first trimester, second trimester, third trimester). Similar analyses will be conducted for pregnancy complications and outcomes among all eligible pregnancies.

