8. RESEARCH QUESTION AND OBJECTIVES

The study will address the question of whether there is an increased risk of MCMs and additional infant/birth and pregnancy outcomes among women between 18 and 49 years of age with IC conditions exposed to HZ/su during pregnancy.

² Self-calculation

214420 (EPI-ZOSTER-039 VS US DB)
Protocol Amendment 2 Final

Primary objective:

1. Evaluate the prevalence of MCMs (as defined in Section 9.3.2.1.1) among live births from women with IC conditions exposed to HZ/su compared to those not exposed to HZ/su during pregnancy.

Secondary objectives:

- 1. Assess the prevalence of additional infant/birth outcomes (preterm birth, small for gestational age (SGA), low birthweight (LBW), neonatal intensive care unit (NICU) admission, neonatal death) among live births in women with IC conditions exposed to HZ/su versus those not exposed to HZ/su during pregnancy.
- 2. Assess the prevalence of pregnancy outcomes (livebirth, stillbirth and spontaneous abortion) and pregnancy complications (placental abruption, preeclampsia and eclampsia) among livebirth and non-livebirth pregnancies in women with IC conditions exposed to HZ/su versus those not exposed to HZ/su during pregnancy.

A feasibility assessment will be conducted (see Section 9.6.1.1). If the feasibility assessment determines that it is not possible to identify an adequate number of exposed live birth pregnancies among women with IC conditions for a cohort study, a descriptive analysis will be conducted. This analysis will describe the prevalence of infant and pregnancy outcomes among exposed and unexposed pregnancies with IC conditions, with no statistical comparisons performed (see Section 9.7.3).

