For analyses evaluating pregnancy outcomes (live birth, non-live births [stillbirth and spontaneous abortion]) and pregnancy complications (placental abruption, preeclampsia and eclampsia) (Secondary Objective 2), the cohort will include pregnancies resulting in a live birth and non-live birth (stillbirth), or spontaneous abortion.

For all analyses, the unit of analysis is a pregnancy episode.

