Pregnancy outcomes will be compared between eligible pregnancies among women with IC conditions who were vaccinated with HZ/su during pregnancy and those who were not vaccinated with HZ/su during pregnancy. Univariate and multivariable statistical analyses will be performed as stated in the primary objective and secondary objective 1 (Section 9.7.2.1) for all outcomes. The prevalence of the pregnancy outcomes (live birth, stillbirth, and spontaneous abortion) and pregnancy complications (placental abruption, preeclampsia and eclampsia) and their 95% CIs will be calculated between the two groups of women. All analyses will be stratified by stage of pregnancy (pre-pregnancy, first trimester, second trimester, third trimester).

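### The protocol gives two conflicting denominators for abruption and preeclampsia/eclampsia, and neither matches a search window that opens at 20 weeks

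*Protocol*

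**What the plan says.** **Search window.** Section 9.3.2.2 states: "Placental abruption (ICD-10-CM O45.X) will be identified by searching the mother's claims from 20 weeks gestation through the date of delivery". The same window is set for preeclampsia and eclampsia, which "will be identified by searching the mother's claims from 20 weeks gestation through the date of delivery". The section also states: "A spontaneous abortion is defined as a spontaneous (non-deliberate) embryonic or fetal death that occurs prior to 20 weeks' gestation". Stillbirth is a fetal death at 20 weeks or later.

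**First denominator: all eligible pregnancies.**
- Section 8, Secondary Objective 2, covers "pregnancy complications (placental abruption, preeclampsia and eclampsia) among livebirth and non-livebirth pregnancies in women with IC conditions".
- Section 9.2.1, naming outcomes and complications together, says "the cohort will include pregnancies resulting in a live birth and non-live birth (stillbirth), or spontaneous abortion".
- The abstract says "Similar analyses will be conducted for pregnancy complications and outcomes among all eligible pregnancies".
- Section 9.7.2.2 plans to calculate "The prevalence of the pregnancy outcomes (live birth, stillbirth, and spontaneous abortion) and pregnancy complications (placental abruption, preeclampsia and eclampsia) and their 95% CIs" in the two groups, with no restriction to pregnancies that reached 20 weeks.

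**Second denominator: linked live births.** The opening of Section 9.7.2 assigns pregnancy complications, together with infant outcomes, to live-birth pregnancies linked to infant records, and keeps the full pregnancy population for pregnancy outcomes only. Section 9.3.2.1, on linked live births, also covers the codes for these complications, and Section 9.3.2.1.7 lists abruption among the infant/birth outcomes.

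**Related rules.** Section 9.2.1.3 requires a comparator to have reached the gestational week of the exposed pregnancy's vaccination without a loss. All analyses are stratified by stage of pregnancy at exposure. If fewer than 237 exposed linked live births are found, Section 9.7.3 limits the report to prevalences and 95% confidence intervals.

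**The concern.** A pregnancy that ends before 20 weeks cannot be a case of either complication under the stated search. If it stays in the denominator, the complication figure mixes two things: how many pregnancies survive to 20 weeks, and how many of those develop the complication. A group difference in early loss then shifts the complication contrast even when the complication risk among pregnancies at risk is the same in both groups. More loss among the exposed pulls the ratio down, and less loss pushes it up.

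If linked live births are used instead, that problem goes away, but pregnancies that are at risk are left out. Until the sections are reconciled, two analysts could follow the protocol and report different prevalences and different contrasts. Under the fallback descriptive analysis the prevalences are the whole result, so the choice of denominator carries more weight there.

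**Working it through.** The protocol states no prevalence, power or expected count for these complications, so there is no figure of its own to reproduce. The check sets the definitions side by side and then works out the algebra.

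**Step 1. Who can be a case.** The window runs from week 20 to delivery. Live births and stillbirths reach week 20; spontaneous abortions, by definition, do not. The at-risk set within the Secondary Objective 2 cohort is therefore live births plus stillbirths.

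**Step 2. All-pregnancy denominator.** Let p be the risk among pregnancies reaching 20 weeks and q the share of the group lost before 20 weeks.
- Prevalence over all pregnancies = p × (1 − q).
- Observed risk ratio = at-risk risk ratio × (1 − q1)/(1 − q0), with 1 for exposed and 0 for unexposed.

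The documents give neither p nor q. With p assumed at 10%:
- q = 5%: 10% × 0.95 = 9.5%
- q = 10%: 10% × 0.90 = 9.0%
- q = 15%: 10% × 0.85 = 8.5%
- q = 20%: 10% × 0.80 = 8.0%

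The relative understatement equals q. For the risk ratio when there is no difference among at-risk pregnancies:
- q0 = q1: factor 1.00
- q0 = 10%, q1 = 15%: 0.85/0.90 = 0.94
- q0 = 10%, q1 = 20%: 0.80/0.90 = 0.89
- q0 = 10%, q1 = 30%: 0.70/0.90 = 0.78
- q0 = 20%, q1 = 10%: 0.90/0.80 = 1.125

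Over assumed ranges of 5–20% for q0 and 5–30% for q1, the factor runs from 0.70/0.95 = 0.74 to 0.95/0.80 = 1.19. As one illustration, a ratio of 1.2 among at-risk pregnancies would appear as 1.2 × 0.75/0.90 = 1.00 if q0 = 10% and q1 = 25%.

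**Step 3. What matching removes.** Because comparators must have reached the exposure week, losses before that week do not create a difference. Losses between exposure and week 20 remain in both groups, so q should be read as loss in that interval. Using the trimester limits in Section 9.2.1.2:
- Pre-pregnancy and first trimester (below 14 weeks): affected.
- Second trimester (14 to below 28 weeks): affected only for exposures before week 20.
- Third trimester (28 weeks on): not affected.

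**Step 4. Linked live-birth denominator.** No spontaneous abortions enter, so the factor in Step 2 does not arise. Stillbirths, which lie within the search window, are excluded. So are unlinked live births: Section 9.2.1 puts linkage at about 74% of infants and Section 9.9.1 at 70–80%. If those figures carry over to this cohort, about 26% (range 20–30%) of live births at risk would be left out, although these complications are found in the mother's claims and need no infant link.

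**The case against.** **The all-pregnancy denominator is not settled.** Section 9.7.2, the parent of the analysis subsections, points to linked live births. A reader might infer that prevalence will certainly be taken over all pregnancies and so will certainly be too low. The documents do not support that: they contradict each other. This part of the objection stands, and the finding is the contradiction plus the mismatch of both versions with the window.

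**The all-pregnancy proportion is a legitimate quantity.** It answers how many of all eligible pregnancies have the complication, and live birth, stillbirth and spontaneous abortion over one denominator form a coherent distribution. This also stands. The figure is low only relative to pregnancies at risk, and it is worth keeping beside the at-risk figure.

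**Restricting to 20 weeks conditions on a post-exposure event.** If vaccination affects early loss, the restricted contrast is open to selection, a concern that Section 9.9.1 raises for infant outcomes. This stands as a cost. It is a reason to report both versions, not to leave the denominator undefined. The linked live-birth version conditions even more strongly.

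**Selection-bias work is deferred to the SAP.** That is so, but the protocol itself fixes the window and both populations, and an SAP that follows it would inherit the conflict.

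**A rise across stages is a weak harm.** A reader might infer that the stage-stratified table will show an artefactual trend. Dilution does lessen with later exposure, but the planned contrast is exposed versus unexposed within stage, and no comparison between stages is planned.

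**Conclusion.** The point holds as a contradiction to be resolved. The protocol names two populations for abruption and preeclampsia/eclampsia, and neither is the set of pregnancies reaching 20 weeks. One includes pregnancies that cannot be cases; the other drops pregnancies that can.

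The size cannot be taken from the documents, because they give no early-loss rate. Under the all-pregnancy version, prevalence falls by the share lost, and the risk ratio is distorted only if loss between exposure and week 20 differs between groups, in either direction. A reader might infer that the vaccine will look protective because exposure is expected mainly in unintended pregnancies. The protocol does expect that pattern of exposure, but nothing in it links such pregnancies to more spontaneous abortion, and Section 9.9.1 says early losses are often not captured.

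Confidence is medium. The outcomes are secondary, and the primary malformation analysis is untouched.

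**What to change.** 1. Reconcile the abstract and Sections 8, 9.2.1 and 9.7.2.2 with the opening of Section 9.7.2, and align Sections 9.3.2.1 and 9.3.2.1.7.
2. In Sections 9.7.2.2 and 9.7.3, compute abruption and preeclampsia/eclampsia among Secondary Objective 2 pregnancies still ongoing at 20 weeks: live births and stillbirths, linked or not.
3. Give stillbirth on that denominator as well as in the all-pregnancy outcome distribution.
4. Report the all-pregnancy complication figures and the exposed–unexposed contrast in spontaneous abortion beside the restricted results.

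The cost is one flag from the gestational length already derived under Section 9.2.1.1, a short text change, and a few extra table rows. The downside is that the restricted estimate is conditional on reaching 20 weeks and some members of matched sets drop out of these outcomes. Item 4 lets the reader judge how much that matters.

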9.3.3. Other Variables (Amended 15 August 2022)

The propensity score reflects the conditional probability of a woman being exposed to HZ/su during pregnancy given baseline potential confounders. Potential confounders to be used in the estimation of the propensity score will be identified in the *273* days prior to the pregnancy start date through the first trimester (period 98 days after the pregnancy start date). This baseline period was selected to provide an adequate covariate evaluation window to capture diagnoses/encounters for most chronic conditions in the health plan

214420 (EPI-ZOSTER-039 VS US DB) Protocol Amendment 2 Final

claims. Diagnoses recorded through the first trimester will be included to account for women who may not have frequent visits prior to pregnancy and may have a more complete assessment of medical conditions during the first prenatal care visit. Separate propensity score models will be fit for the cohorts of eligible live birth pregnancies and cohorts of all eligible pregnancies. Information about variables that may predict the likelihood of exposure will be collected from health plan claims data. These variables will include maternal age, calendar year, maternal comorbidities (Appendix I:. Maternal Comorbidities), tobacco use, alcohol use, drug dependence, maternal obesity, and maternal race/ethnicity, and U.S. region of residence (Midwest, West, South, Northeast). In addition, the number of healthcare encounters (outpatient, emergency department, inpatient) in the 273 days preceding the pregnancy start date will be identified.

The propensity score model will be fit separately for each DP and matching on the propensity score will occur within DP. The propensity score will be calculated by each DP using logistic regression. The main reason to use DP-specific propensity score is to protect sensitive individual and institutional information. It is also desirable to generate and match propensity scores within DP and match within DP because DP can be representative of background variables at the DP level (e.g., insurance coverage), which will not be available at individual level. The large number of enrollees of each DP is additional assurance that the best control will be within DP. Further description of the analytical steps of the data is provided in the SAP.

At least 15 FDA sponsored Sentinel safety studies were displayed when searching the keyword "propensity score" in the referenced web address using a similar propensity score matching approach with multiple DPs. Two examples are provided here:

- 1. Sixteen DPs participated in an analysis assessing the risk of cutaneous small-vessel vasculitis associated with the use of direct oral anticoagulant and warfarin among patients with atrial fibrillation aged 21 to 99 years. The final report is provided on the Sentinel web site.
- 2. Four DPs participated in a study estimating the risk of intentional self-harm and hospitalized depression comparing brand name sertraline to its authorized generic using. Four reports are provided on the Sentinel web site.

Because nearest neighbor matching tends to result in less biased estimates compared with the other matching algorithms [Austin, 2014], Sentinel developed SAS macros to facilitate such a matching algorithm. The general framework of using distributed network to conduct propensity score matching and distributed regression analysis has been developed by Sentinel [Toh, 2020] and used extensively for Federal or Patient-Centered Outcomes Research Institute (PCORI) sponsored comparative effectiveness and safetystudies [Toh, 2020].

9.4. Data sources

This study will be conducted using health plan data held by three DPs (CVS Health CTS, HealthCore, and Optum) that are national insurers participating in the FDA's Sentinel System. In addition to providing claims data, the DPs will provide scientific input and feedback to support this study. All participating DPs have experience in previous pregnancy exposures studies and other HZ/su studies. In addition, all have experience in linking pregnant women with their infants within the database.

The Sentinel System is an active surveillance system that uses routine querying and analytical tools to evaluate electronic healthcare data from a distributed data network for monitoring the safety of regulated medical products in the United States, established under the Sentinel Initiative [Bateman, 2021; Platt, 2018].

The average enrollment length for patients across data sources in Sentinel is similar to other claims databases of members with medical and pharmacy coverage. About 25% of patients have over three years of enrollment, and patients with chronic conditions such as diabetes and older members typically have longer than average enrollment periods within these databases.

Brief descriptions of the DPs are provided below:

- CVS Health is one of the nation's leading healthcare benefits companies, serving 38 million people with information and resources to help them make better-informed decisions about their healthcare. CVS Health CTS became an FDA Sentinel DP in 2010 and continues to be one of the largest contributors of data for public health purposes.
- **HealthCore, Inc.**, a wholly owned subsidiary of Anthem, Inc., uses real-world data to conduct outcomes, health economics, pharmacoepidemiologic, and late phase research. The HealthCore Integrated Research Database is a proprietary, fully integrated, longitudinal claims database that combines medical, pharmacy, and laboratory information drawn from 72.5 million unique individuals with medical coverage and more than 51 million individuals with medical and pharmacy claims information since 2006. In addition, The HealthCore Integrated Research Environment has the ability to link claims data in the HealthCore Integrated Research Database to complementary data sources, including inpatient and outpatient medical records, national vital statistics records, cancer and vaccine registries (state-by-state), disease and device registries, member and provider surveys, and point of care clinical data. Using these resources, HealthCore conducts a range of real-world research designed to meet client needs, including retrospective database studies, medical record review studies, cross-sectional and longitudinal patient and provider surveys, and prospective site-based studies, including pragmatic clinical trials.
- **Optum** (**UnitedHealth**). Initially founded as Epidemiology Research Institute, and later acquired in 1999 by Ingenix (renamed to Optum), Optum Epidemiology has a nearly 40-year history in regulatory drug safety research. Optum Epidemiology scientists leverage their extensive applied experience with real world data sources to inform the design and implementation of clinical and pharmacoepidemiology

214420 (EPI-ZOSTER-039 VS US DB) Protocol Amendment 2 Final

research; safety profile and effectiveness evaluations; and risk assessment. Optum's rich data assets include the Optum Research Database comprised of administrative claims data from health plans of a large U.S. national health insurer, with data beginning in 1993. For 2017, data are available for approximately 14.6 million commercially insured individuals with medical and pharmacy coverage. Additional Optum data assets include Electronic Health Records.

The DPs use the Sentinel Common Data Model (SCDM) for standardization of demographic and clinical data elements [Curtis, 2012; Sentinel]. Publicly available routine analytical tools include reusable, modular Statistical Analysis System (SAS) programs. These analytical tools are designed to be executed against the SCDM to permit rapid queries, including descriptive analyses and complex methodologies (e.g., comparative analyses), across DPs. Specific information in the SCDM includes, but is not limited to, the following types of data:

- Enrollment data: One record per covered individual per unique enrollment span is included in the SCDM. Individuals are assigned a unique identifier by their insurer, which is linkable to all other data in the SCDM. Due to changes in employment status, individuals may be enrolled multiple times with the same insurer, and the length of each given enrollment "span" may vary substantially. Each record in the enrollment file indicates the patient identifier, enrollment start and end dates, and whether the patient was enrolled in medical coverage, pharmacy coverage, or both during that range. Likewise, a final field indicates whether the DP can request medical charts for a given patient during a given enrollment span.
- **Demographic data**, including birth date, sex, race/ethnicity, and ZIP code of their most recently recorded primary residence.
- Pharmacy dispensing data, including the date and NDC identifier for each dispensed prescription, the nominal days' supply, and the number of individual units (pills, tables, vials, etc.) dispensed. Products purchased over-the-counter or at some cash-only retail locations selling prescription drug products (e.g., through the Walmart Prescription Program) are not captured.
- Medical encounter data, including the healthcare provider most responsible for the encounter as well as the facility in which the encounter occurred and its ZIP code. Admission and discharge dates (if applicable) are also included, as is the encounter type (either an ambulatory visit, an emergency department visit, an inpatient hospital stay, a non-acute inpatient stay, or an otherwise unspecified ambulatory visit). Discharge disposition (alive, expired, or unknown) as well as discharge status (to where a patient was discharged) are also included for inpatient hospital stays and non-acute inpatient stays. Finally, laboratory data are available for some, but not all, of the DPs; and the level of completeness for laboratory information for those DPs with such data varies [Raebel, 2014].
- Diagnosis data, including the date of diagnosis, its associated encounter identifier, admission date, provider identifier, and encounter type. Diagnoses are recorded with ICD-9-CM and ICD-10-CM codes. For inpatient hospital and non-acute inpatient stay encounters, the SCDM includes both principal and non-principal discharge diagnosis data. Outcomes and covariates will be identified using ICD-10 codes.

214420 (EPI-ZOSTER-039 VS US DB)
Protocol Amendment 2 Final

Procedure data, including the procedure date, its associated encounter identifier, admission date, provider identifier, and encounter type. Procedures are coded as ICD-9-CM and ICD-10-CM Procedure Coding System procedure codes, CPT categories II, III, or IV codes, revenue codes, as well as HCPCS levels II and III codes. ICD-10-CM Procedure Coding System and CPT codes will be used for the analysis.

In addition to access to health plan claims data, all DPs have experience in medical chart retrieval procedures. The expected timeline for chart retrieval is generally between 3 to 6 months, depending on the facility/provider's willingness to participate. Many factors affect retrieval, including the number of facilities/providers to which outreach must be conducted, the type of chart (inpatient vs. ambulatory and whether an electronic health record (EHR) is accessible), and how far back records are requested. We expect chart reviews to be conducted for approximately 5% of pregnancies based on validation studies [Andrade, 2013; Cheetham, 2020; Cooper, 2008; Hansen, 2016; He, 2020]. It is anticipated that approximately 70-85% of requested charts will be returned with enough information (i.e., complete chart) to determine the presence or absence of MCM. Typically, the completeness of medical chart retrieval depends on the type of chart, the facility/provider, how many charts requested, and the type of information.

